6.1.3 Treatment Discontinuation

The number and percentages of participants who ended product use early, as well as the reason for terminating product use early, will be presented in a table overall and by site and in a table overall and by randomized sequence.

6.1.4 Study Discontinuation

The number and percentages of participants who completed the study, as well as the reasons for non-completion, will be displayed in a table overall and by site.

6.1.5 Completion of Procedures

The completion of required and expected procedures will be displayed in a table overall and by site. The table will display the number and percentages of participant-visits for each procedure.

6.2 Treatment Exposure

The number and percentage of participants who received each of the three study products, along with the number and percentage of participants who completed the corresponding product use end visit (PUEV) will be displayed in a table overall and by site, and in a table overall and by randomized sequence. In addition, the number and percentage of participants who received all three study products and completed all three PUEV will also be displayed.

6.3 Protocol Deviations

Protocol deviations occurring in MTN-035 will be summarized in a table for each type of deviation, overall and by site, and in a listing of deviation events.

7. BASELINE DATA

Baseline demographic characteristics of the participants, such as age, age group, sex at birth, gender, ethnicity (U.S sites), race (U.S sites), ethnic group or tribe (international sites) will be summarized and displayed in a table overall and by site, and in a table overall and by randomized sequence. Descriptive statistics will be presented for age. Frequency counts and percentages will be presented for age group, sex at birth, gender, ethnicity (U.S sites), race (U.S sites), ethnic group or tribe (international sites). No formal comparisons are planned.

Other individual characteristics of the participants at baseline, including baseline medical history, baseline rectal exam findings, and baseline STI findings, will be presented in listings if applicable.

8. PRIMARY ENDPOINTS

The acceptability, tolerability and adherence primary endpoints will be evaluated on the per-protocol subset of participants, i.e. participants who received all three study products and completed the corresponding PUEV, and thus provide relevant data from all three periods of study. Assessment of these endpoints will be based on responses from the participants to the computer assisted self-interviews (CASI) at the three PUEVs (Visits 3, 5 and 7). To aid in the interpretation of the resulting analyses, baseline characteristics of the per-protocol subset of participants including, but not limited to, study site, sequence, sex/gender, and age will be described and compared to those of participants who were lost to follow-up.

Acceptability and Tolerability

The acceptability and tolerability endpoint will be based on question H1 of the CASI:

“Think about the positive and negative experiences you have had using the rectal Insert during the past 4 week period. If this rectal insert was available and it provided some protection against HIV, how likely would you be to use it before receptive anal sex?”.

Responses to this question for each product were captured from visual Likert scale from 1 (very unlikely) to 10 (very likely). Participants’ responses corresponding to the three product use periods will be displayed in tables by study product, by study product and site and by study product and randomization sequence.

To compare acceptability and tolerability between study products, the endpoint will be operationalized as binary, with scores 1 to 6 grouped as “low acceptability” and scores 7 – 10 as “high acceptability”. Number and percentage of participants giving a “high acceptability” score will be display in tables by study product, with exact binomial 95% confidence intervals (Clopper-Pearson method).

Adherence

Two endpoints related to adherence will be assessed: adherence to use per-protocol and adherence to use per-anal-sex-act. These are defined as follows:

1. **Adherence to use per-protocol:** Number and proportion of participants who reported not having missed a rectal [enema/douche, insert or suppository] application in the previous 4 weeks, according to the participants’ response to question B0 of the CASI:

B0. The following questions refer to your use of the study provided rectal [**study product: douche/enema, insert or suppository**] over the past 4 weeks. You were asked to insert the study provided rectal [**study product**] in your rectum at least once a week during the past 4 weeks. However, for different reasons, people might have encountered difficulties using the [**study product**]. Thinking about your experience during these past four weeks, in how many of the weeks did you miss a rectal [**study product**] application?

- 0 weeks
- 1 week
- 2 weeks
- 3 weeks
- 4 weeks

Responses to question B0 will be tabulated by study product, study product and sequence and study product and site, along with the number and proportion of participants fully adherent (those

who reported 0 weeks missing application), with 95% confidence intervals (Clopper- Pearson). If needed, additional categories of invalid/missing responses will be included.

- 2. Adherence per sex-act:** Proportion of times when participants reported having used the study-provided rectal douche/enema, insert or suppository before receptive anal sex. For participants who reported at least 1 anal sex act in the previous 4 weeks, this proportion will be obtained by dividing the number reported in Question B2 over the number reported in Question B1 of the CASI:

B1. How many times did a partner put a penis in your rectum during the past 4 weeks?

B2. Of those [] times, how many times did you use the study-provided rectal **[study product: douche/enema, insert or suppository]** BEFORE receptive anal sex? (If you did not use the douche prior to anal sex, please enter '0'.)

Responses to Questions B1 and B2 will be cross tabulated, by study product and by study product and site. If needed, additional categories of invalid/missing responses will be included. Summary statistics (mean and SD, median and IQR) of participants' per sex-act adherence, as defined above, will be displayed by study product and by study product and site.

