## **10.2 Study Endpoints**

Consistent with the primary study objective to evaluate the acceptability and tolerability of a placebo insert, a placebo douche, and a placebo suppository when applied rectally and used prior to RAI, the following endpoints will be assessed on a scale of 1 to 10 for each study product:

- Participant self-report of likelihood of product use if shown to be effective

Consistent with the primary study objective to evaluate adherence to a placebo insert, a placebo douche, and a placebo suppository when applied rectally and used prior to RAI over a 4-week-long period, the following endpoints will be assessed for each study product:

- Per participant report, percentage of occasions when study product was used as instructed (per protocol)

Consistent with the primary study objective to evaluate the safety of a placebo insert, a placebo douche, and a placebo suppository when applied rectally and used prior to RAI, the following endpoints will be assessed for each study product:

- Grade 2 or higher related AEs as defined by the Division of AIDS Table for Grading the Severity of Adult and Pediatric Adverse Events, Corrected Version 2.1, July 2017, and/or Addenda 1, 2 and 3 (Female Genital [Dated November 2007], Male Genital [Dated November 2007] and Rectal [Clarification Dated May 2012] Grading Tables for Use in Microbicide Studies)

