## **10.7 Data Analyses**

### **10.7.1 Primary Analyses on Acceptability/Tolerability and Adherence Measures**

All primary analyses will be based on data from the participants with data in all three periods of study (participants who complete each period of the study). Baseline values between these participants and those participants lost to follow-up will be described and used to interpret the generalizability of the results. Additionally, secondary analyses will analyze endpoints among all participants. The adherence and acceptability/tolerability endpoints (defined in Section 10.3.1) will be reported with 95% CI. The purpose of this protocol is not to compare the placebo products; therefore, we do not plan on doing comparisons between products in the primary analysis. Logistic regression models will be used to assess the order of product use (period effect) on acceptability/tolerance and adherence.

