2.2 Study Objectives and Endpoints

Primary Objectives:

Acceptability and Tolerability

- To evaluate the acceptability and tolerability of each study product when applied rectally and used prior to RAI
 - Placebo rectal insert
 - Placebo rectal douche
 - Placebo rectal suppository

Adherence

- To evaluate adherence to each study product prior to RAI over a 4-week-long period
 - Placebo rectal insert
 - Placebo rectal douche
 - Placebo rectal suppository

Exploratory Objective:

Relative Acceptability and Tolerability

- To evaluate the relative acceptability and tolerability between study products when applied rectally and used prior to RAI
 - Placebo rectal insert
 - Placebo rectal douche
 - Placebo rectal suppository

Primary Endpoints:

Acceptability and Tolerability

- For each study product, participant self-report of likelihood of product use if shown to be effective

Adherence

- Per participant report, percentage of occasions when each study product was used as instructed (per protocol)

Safety

- Grade 2 or higher related adverse events (AEs) as defined by the Division of AIDS Table for Grading the Severity of Adult and Pediatric Adverse Events, Corrected Version 2.1, July 2017, and/or Addenda 1, 2 and 3 (Female Genital [Dated November 2007], Male Genital [Dated November 2007] and Rectal [Clarification Dated May 2012] Grading Tables for Use in Microbicide Studies)

Exploratory Endpoint:

Relative Acceptability and Tolerability

- Conjoint analysis of participant acceptability and tolerability between the three study products

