2.5 Sample Size and Power

There is no control group for comparison in this study. The goal is not to compare each product to some standard but instead to estimate overall rates of acceptability, adherence and safety.

Primary Endpoints – Acceptability/Tolerability and Adherence

Based on previous studies we expect to observe a high rate of acceptability (>80%) which equates to $\leq 20\%$ of participants reporting a low likelihood of using the product in the future (≤ 3 on the rating scale). Likewise, we expect to observe a high rate of participants reporting taking at least 90% of expected doses.

The table below shows the exact confidence intervals for acceptability and adherence, assuming $\alpha=0.05$ based on the Binomial distribution and varying rates of acceptability and adherence. The power to rule out <50% and <70% acceptability or adherence given the rates is also shown. Calculations assume the outcomes are observed in 200 of the participants (5% loss to follow-up). For example, if the true acceptability or adherence rate is 90%, we have 100% power to rule out a true acceptability or adherence rate of 75% or lower. If we observe an 80% acceptability or adherence rate, the corresponding 95% confidence interval (CI) will be (74%, 85%).

Table 2: Exact 2-sided 95% Confidence Intervals Based on Various Rates of Acceptability or Adherence Endpoints

Acceptability rate / adherence rate	95% CI if rate is observed	Power to rule out 50% if rate is true	Power to rule out 70% if rate is true	Power to rule out 75% if rate is true
95%	(91, 98)	100%	100%	100%
90%	(85, 94)	100%	100%	100%
85%	(79, 90)	100%	100%	93%
80%	(74, 85)	100%	90%	35%

Primary Endpoint – Safety

To characterize the statistical properties of the safety endpoint, the table below presents the probability of observing zero, at least one, and two or more safety endpoints among 200 participants (allowing for the possibility of 5% dropout) assuming various “true” event rates. By assuming that we may only have safety evaluations on 200 participants, these calculations are conservative. However, safety analyses will include all enrolled participants.

Table 3: Analysis of Safety Event Frequency

Event Rate	P(0 events n=200)	P(≥ 1 event n=200)	P(≥ 5 events n=200)	P(≥ 10 events n=200)
0.1%	82%	18%	0%	0%
0.5%	37%	63%	0%	0%
1%	13%	87%	5%	0%
2%	2%	98%	37%	1%
5%	0%	100%	97%	55%

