9.3 Other Safety Measures

Additional safety summaries include:

The number and percentage of participants with a positive result for hCG for pregnancy and HIV will be displayed in a table overall and by site if applicable. A listing of participants with positive results of STI testing (syphilis, trichomonas, gonorrhea, chlamydia) after first study product use will be presented if applicable.

A listing of participants with abnormal findings on rectal exam after first study product used will be presented.

A listing of all concomitant medications will be presented.

10. Exploratory Analysis

In addition to the analyses described above, the following analyses will be conducted to compare and estimate the relative acceptability/tolerance, adherence and safety between the three study products. These analyses will also allow to assess potential effects of the order of product use on each of the endpoints.

A logistic mixed effects regression model will be used to estimate the relative odds (odds ratios) of high acceptability between the different study products. A similar logistic mixed effects regression model will be used to estimate the relative odds (odds ratio) of full per-protocol and per-sex-act adherence between the different study products. To account for the cross-over design of the study, a random intercept at the participant level will be included in the models. Estimates of the odds-ratios, along with 95% confidence intervals and associated p-values will be reported. If feasible, testing for effects of the order of product use will be done by including interaction terms between study product and randomized sequence in the model.

A logistic mixed effects regression model will be used to estimate the relative odds (odds ratio) of having a primary safety endpoint, as defined in section 9.1, between the different study products. A Poisson mixed effects regression model will be used to compare the incidence (expected counts) of AEs per study period between the study products. If feasible, interaction terms between study product and randomized sequence will be included in the model to test the effect of order of product use on the safety endpoints.

11. References

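### SAP 8 counts scores 1–6 as low acceptability, where protocol 10.3.1 and SAP 2.5 count 3 or less; the change is not declared and no interval is planned for the protocol's 4–10 rate

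*SAP*

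**What the plan says.** The endpoint itself has no threshold. SAP 2.2 describes it as "participant self-report of likelihood of product use if shown to be effective", and protocol 10.2 says "the following endpoints will be assessed on a scale of 1 to 10 for each study product".

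A threshold enters in protocol 10.3.1, which SAP 2.5 repeats. Acceptability above 80% is equated there with at most 20% "of participants reporting a low likelihood of using the product in the future", and low is set at 3 or less. Protocol 10.7.1 then carries that definition into the primary analysis: "The adherence and acceptability/tolerability endpoints (defined in Section 10.3.1) will be reported with 95% CI".

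SAP 8 keeps the same item and scale. It first states that participants' "responses corresponding to the three product use periods will be displayed in tables by study product", and also by site and by sequence. It then turns to comparing products, for which "the endpoint will be operationalized as binary, with scores 1 to 6 grouped as" low acceptability and scores of 7 to 10 as high. The number and percentage scoring 7–10 are given by product with Clopper-Pearson 95% intervals. No other acceptability rate receives an interval. SAP 10 takes the same split into a mixed logistic model "used to estimate the relative odds (odds ratios) of high acceptability between the different study products".

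**The concern.** One SAP gives two meanings to low for the same primary endpoint: 3 or less in section 2.5 and 6 or less in section 8. Scores 4, 5 and 6 change sides between them. The body of the SAP does not acknowledge the change, say why 7 was chosen, or say when. The timing matters because the study is open label (SAP 2.4).

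Two things are at stake. First, the rate and interval that protocol 10.7.1 calls for are not a planned output. Both documents state that the aim is to estimate rates, so the interval is the main inferential result for this endpoint. Second, the only rate printed with an interval is for 7–10, while the only stated expectation, above 80%, was written for 4–10. A reader who sets one against the other can err in one direction only: a product that meets the expectation may look as though it falls short.

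**Working it through.** **Inputs**

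- Scale 1–10 for each product: protocol 10.2, SAP 8.
- Low = 3 or less, hence acceptable = 4–10 as the complement: protocol 10.3.1, SAP 2.5.
- Low = 1–6, high = 7–10: SAP 8.
- Planning n = 200, two-sided exact 95% intervals: protocol 10.3.1, SAP 2.5 (210 × 0.95 = 199.5).
- Share scoring 4–6: not given in the documents, so it is assumed and varied.

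**Step 1: reproduce the plan's own table (protocol Table 9, SAP Table 2)**

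For x successes out of n, the Clopper-Pearson limits are:

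- lower = Beta quantile(0.025; x, n − x + 1)
- upper = Beta quantile(0.975; x + 1, n − x)

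| Observed rate | x/200 | Computed CI (%) | Stated CI (%) |
|---|---|---|---|
| 95% | 190 | 91.0–97.6 | 91–98 |
| 90% | 180 | 85.0–93.8 | 85–94 |
| 85% | 170 | 79.3–89.6 | 79–90 |
| 80% | 160 | 73.8–85.3 | 74–85 |

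Power is P(X ≥ r), where r is the smallest count whose lower limit exceeds the excluded rate: r = 115 for 50%, 153 for 70% and 163 for 75%. All 12 cells come within 2 points of the stated values. The three furthest from a trivial 100% are:

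- 85% against 75%: 92.8% (stated 93%)
- 80% against 70%: 90.6% (stated 90%)
- 80% against 75%: 33.5% (stated 35%)

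The table is sound, and it holds for any binary rate at n=200 whichever cut defines it. What does not carry over to the new cut is the expectation above 80%.

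**Step 2: relate the two rates**

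P(7–10) = P(4–10) − P(4–6)

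The gap is the share scoring 4–6. It cannot be negative.

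**Step 3: illustrate at n=200**

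| Assumed 4–6 share | 7–10 rate (CI) if 80% score 4+ | 7–10 rate (CI) if 90% score 4+ |
|---|---|---|
| 0% | 80% (73.8–85.3) | 90% (85.0–93.8) |
| 5% | 75% (68.4–80.8) | 85% (79.3–89.6) |
| 10% | 70% (63.1–76.3) | 80% (73.8–85.3) |
| 20% | 60% (52.9–66.8) | 70% (63.1–76.3) |

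**Step 4: when does the whole 7–10 interval fall below 80%?**

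This yardstick is chosen here for scale; neither document uses it. The upper limit is 80.4% at 149/200 and 79.9% at 148/200 (74.0%, CI 67.3–79.9), so the condition is met at 148 or fewer.

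- If 80% score 4 or more: 80 − 74 = 6 points in scores 4–6.
- If 90% score 4 or more: 90 − 74 = 16 points.

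**The case against.** The strongest reply is that the 3-or-less figure belongs to a sample-size paragraph. The endpoint sections carry no cut, and 4–10 as acceptable is never written out; it is only the complement of low. On this view SAP 8 is the operational definition, and the reference in protocol 10.7.1 may be loose, since the parallel safety paragraph in 10.7.2 points to section 10.2. That would be persuasive without 10.7.1. Read literally, though, that sentence sits in the primary analysis section and makes 10.3.1 the source of the definition.

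It can also be said that the 7–10 split serves product comparison. SAP 8 does introduce it that way. But it appears under primary endpoints and is the only acceptability rate with an interval, while protocol 10.7.1 keeps product comparisons out of the primary analysis.

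The information is largely preserved. SAP 8 displays the responses by product, and SAP 5 gives counts and percentages per category for categorical variables. If the item is treated as categorical, the 4–10 count follows directly. If it is summarised as continuous, it may not. In neither case is an interval for 4–10 planned.

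Three points stand in full. The new cut is stricter, so it cannot flatter a product. A cut at 4 is lenient, and 7–10 is a defensible choice. And no product is tested against a standard, so the 80% figure is an expectation and not a success criterion. These limit the weight of the point but do not reconcile the sections.

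**Conclusion.** The point holds and should be fixed. SAP 8 departs from the cut in protocol 10.3.1 and SAP 2.5, and it plans no interval for the rate to which protocol 10.7.1 attaches one. That the change is undeclared is judged on the body of the SAP.

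The numerical effect equals the share scoring 4–6, which is unknown. It is nil if nobody scores there. The figures above rest on assumed shares and on the planning n of 200; the actual denominator will be the participants who received all three products and completed all three product use end visits (SAP 3.1). The fault is an inconsistent definition and a missing interval. It does not inflate a result, and no planned decision depends on it.

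**What to change.** In SAP 8:

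- Report, by product, the number and proportion scoring 4 or more with a Clopper-Pearson 95% interval, labelled as the protocol-defined rate. Note that the expectation above 80% was written for this rate. That is a descriptive reading and adds no test.
- Keep the 7–10 rate and its interval beside it, labelled as an additional result that also feeds the SAP 10 models.
- State that responses to H1 are shown as counts at each score.
- State that 7–10 differs from the cut in protocol 10.3.1 and SAP 2.5, give the reason and when it was chosen, and say that the 80% expectation does not apply to it.

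The cost is a few sentences and one extra row per table, with no new data. SAP 8 already uses this layout for adherence: "Responses to question B0 will be tabulated by study product", followed by a binary rate with an exact interval. Because a cut at 4 is lenient, showing both rates is more informative than replacing one with the other.

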#### **10.3.1 Primary Endpoints – Acceptability/Tolerability and Adherence**

Based on previous studies we expect to observe a high rate of acceptability (>80%) which equates to  $\leq 20\%$  of participants reporting a low likelihood of using the product in the future ( $\leq 3$  on the rating scale). Likewise, we expect to observe a high rate of participants reporting taking at least 90% of expected doses.

The table below shows the exact confidence intervals for acceptability and adherence, assuming  $\alpha=0.05$  based on the Binomial distribution and varying rates of acceptability and adherence. The power to rule out  $<50\%$  and  $<70\%$  acceptability or adherence given the rates is also shown. Calculations assume the outcomes are observed in 200 of the participants (5% loss to follow-up). For example, if the true acceptability or adherence rate is 90%, we have 100% power to rule out a true acceptability or adherence rate of 75% or lower. If we observe an 80% acceptability or adherence rate, the corresponding 95% confidence interval (CI) will be (74%, 85%).

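### SAP 8 gives a confidence interval to neither Protocol form of the adherence endpoint; its only adherence percentage with one is zero missed weeks on CASI B0, labelled per-protocol

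*SAP*

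**What the plan says.** **What is to be reported.** Protocol 10.7.1: "The adherence and acceptability/tolerability endpoints (defined in Section 10.3.1) will be reported with 95% CI". The only adherence statistic in Protocol 10.3.1 is in the sentence "we expect to observe a high rate of participants reporting taking at least 90% of expected doses", and SAP 2.5 repeats that sentence with the same precision table.

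**How the endpoint is listed.** Protocol 10.2 gives it as "percentage of occasions when study product was used as instructed (per protocol", and SAP 2.2 agrees.

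**What SAP 8 analyses.** The source is the CASI: "Assessment of these endpoints will be based on responses from the participants to the computer assisted self-interviews (CASI". Two adherence measures follow.

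- The first, named adherence to use per-protocol, is "Number and proportion of participants who reported not having missed a rectal [enema/douche, insert or suppository] application in the previous 4 weeks". It comes from question B0, which reminds participants that they were asked to insert the product "in your rectum at least once a week during the past 4 weeks" and asks in how many weeks they missed an application. It has a Clopper-Pearson 95% CI.
- The second is adherence per sex act, B2/B1. It is restricted: "For participants who reported at least 1 anal sex act in the previous 4 weeks". It gets a cross-tabulation of B1 by B2, with mean and SD and median and IQR.

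SAP 10 adds odds ratios between products for full adherence on both measures.

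**What participants were told.** The Protocol Summary (Study Regimen) asks for use before each RAI encounter, and for use without sex in a week that has no RAI.

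**The concern.** Adherence is one of the primary objectives, and the study exists to estimate rates. The statistic that 10.7.1 points to for a CI appears nowhere in SAP 8 or 10: no planned analysis counts expected doses or applies a 90% threshold. The endpoint as listed in 10.2 and SAP 2.2 is best approximated by B2/B1, and that has no CI either. So on either reading of the Protocol, the adherence endpoint lacks its interval, and the SAP neither states nor justifies the change.

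The measure that does get a CI carries the per-protocol name, but it counts weeks against a once-a-week reference rather than doses against the full instruction. A reader of the final tables could take it as the rate of following the regimen.

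**Working it through.** **1. The plan's own figures.** Clopper-Pearson at n = 200, with 160 successes (80%), gives (73.8%, 85.3%); the plan states (74, 85). Power is the probability of reaching the smallest count whose lower limit exceeds the null rate:

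- 80% against 70%: 153 or more, 90.6% (stated 90%).
- 80% against 75%: 163 or more, 33.5% (stated 35%).
- 85% against 75%: 92.8% (stated 93%).

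The table reproduces closely. It holds for any binary rate observed in 200 participants, so the choice of adherence measure does not affect it.

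**2. The 90% rule in whole doses (no assumption).** With n expected doses, the rule requires ceil(0.9n).

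- n = 4 to 9: all n (8 of 9 = 89% fails).
- n = 10 to 19: one miss allowed (9 of 10 = 90%).

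**3. B0 against the rule.** B0 can be read in two ways.

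- *Strict: any due dose missed that week.* Zero missed weeks means every dose taken. This equals the 90% rule below 10 expected doses and can only be lower from 10 up. Example: 11 of 12 (92%) meets the rule and fails B0.
- *Literal: no use at all that week.* This equals the rule at 4 expected doses (one per week) and can be higher from 5 up. Example: 4 of 12 (33%), one each week, passes B0. From 10 up it can also be lower for an individual: 9 of 10 fails if the one missed dose was the only one due that week.

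**4. B2/B1 against the rule.** It leaves out participants with no acts and all doses due in weeks without RAI. B0, B1 and B2 do not record in which weeks acts fell, so expected doses cannot be computed from them.

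**5. Illustrative size.** The documents give no RAI rate except the entry minimum of three acts in three months (Protocol 5.2), taken here as 3/13 per week. Assumptions, for this calculation only: weekly acts k are Poisson; doses due in a week are max(k, 1); each is taken independently with probability p. With n the four-week total due and d the doses due in one week:

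- 90% rule = P(Binomial(n, p) ≥ ceil(0.9n)), averaged over n
- B0 strict = [E(p^d)]^4
- B0 literal = [E(1 − (1 − p)^d)]^4
- B2/B1 of at least 90% = the same binomial tail over four-week acts, given at least one act

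Percentages at p = 0.90:

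| RAI per week | Mean due | 10 or more due | 90% rule | B0 strict | B0 literal | B2/B1 ≥ 90%, if any act |
|---|---|---|---|---|---|---|
| 3/13 | 4.1 | <0.1 | 65.0 | 65.0 | 66.2 | 85.4 |
| 1 | 5.5 | 1 | 57.3 | 56.8 | 73.1 | 66.7 |
| 2 | 8.5 | 32 | 54.2 | 42.0 | 83.7 | 55.6 |
| 3 | 12.2 | 78 | 58.0 | 29.3 | 91.3 | 57.8 |

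Range over p (rule, strict, literal):

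- 3/13 per week: 40.2, 40.2, 41.7 at p = 0.80; 81.1, 81.1, 81.8 at p = 0.95.
- 3 per week: 22.7, 8.4, 81.1 at p = 0.80; 82.0, 54.2, 95.8 at p = 0.95.

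At the entry minimum, exp(−4 × 3/13) = 39.7% have no act in four weeks and drop out of B2/B1. That is why its 85.4% is far from the rule's 65.0%, and why it cannot stand in for the rule.

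**6. Sensitivity to the 24-hour advice in Protocol 6.2.** Count at most one due dose per day, each day with probability 1 − exp(−rate/7). At 2 and 3 acts per week, the share with 10 or more due falls to 15% and 56%. At p = 0.90 the strict shortfall falls from 12.2 to 5.9 points and from 28.7 to 21.1. The literal excess stays at about 30 and 33 points.

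**The case against.** - **The undertaking rests on one cross-reference.** Section 10.3.1 is a sample-size section and words the 90% figure as an expectation. The endpoint section is 10.2, which gives percentage of occasions, and B2/B1 measures nearly that. This stands: the documents do not support inferring that the Protocol fixed a 90% responder endpoint beyond doubt, or that the SAP leaves primary adherence unanalysed. What remains is that 10.7.1 still names 10.3.1 as the definition, and that the 10.2 form has no CI either.
- **The precision table still has a match.** A reader might infer that it is left without an adherence result. It is not: the table is generic, and the B0 proportion with its exact interval is a rate of that kind. The mismatch is one of definition.
- **The label is open to view.** SAP 8 prints B0 in full beside the name, and its definition of the measure favours the strict reading, under which B0 equals the 90% rule below 10 doses and errs only downwards above that. This softens the point. But the question's own once-a-week wording invites the literal reading, and the documents do not show which one participants used.
- **The large gaps are modelled.** Rates of 2 and 3 per week are about 9 and 13 times the entry minimum. That is correct. A claim that B0 inflates or seriously misstates adherence in this trial is not supported.
- **The counts can be recovered.** The B1 by B2 cross-tabulation lets a reader work out the share at 90% of acts, but only without a planned interval and with the omissions in step 4. The odds ratios in SAP 10 compare products; they do not estimate a rate.

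**Conclusion.** The point holds as a reporting gap that should be fixed. SAP 8 attaches a CI to neither the 90%-of-expected-doses share nor the percentage of occasions. It attaches one to a weeks-missed answer under the per-protocol name, without stating the departure.

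This rests on the text and the whole-dose arithmetic, not on the model. The size and direction of the difference are unknown, because neither the RAI rate nor how participants read B0 is given. Under the stated model, B0 differs from the 90% rule at the entry-minimum rate by 0 to 1.2 points at 90% use, and by at most 1.5 points over 80% to 95% use. At 3 acts per week and 90% use it could lie anywhere from 28.7 points below to 33.3 points above. The adherence objective is not lost and the sample-size calculation stands.

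**What to change.** In SAP 8:

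1. Rename the B0 measure 'no missed weeks (CASI B0)' and keep its CI.
2. Add, by product, a 95% CI for mean B2/B1, and the share of participants with B2/B1 of at least 90% with a Clopper-Pearson CI. State how many were excluded for reporting no acts.
3. Present B0 and B2/B1 side by side, neither as a substitute for the 90%-of-expected-doses rate, and state the departure from Protocol 10.3.1.
4. Reconcile the Protocol Summary regimen, Protocol 6.2, 6.2.1, 6.2.2, 10.2 and 10.3.1, and the CASI items in SAP 8, so that expected doses and the adherence endpoint each have one definition. In particular, 6.2.1 (insert, suppository) and 6.2.2 (douche) give different instructions after a missed dose. Only after that, and if the weekly SMS/IM items allow it (Protocol 7.4.1 and 7.8 describe these reports but do not show the items), add the share with at least 90% of expected doses with an exact CI, and amend the sentence that confines these endpoints to the CASI.

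Steps 1 to 3 cost wording and a few intervals from data already collected. Step 4 needs a decision by the protocol team and, if feasible, one derived variable. The reported adherence figure may move either way.
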